1.0 Study Summary

Study Title	Defense Cascade: Physiology, Mobility, and Subjective Experience
Study Design	In-lab virtual reality (VR) stimuli will be presented for this psychophysiology study with online prescreen. Data will be analyzed using correlational analyses and OLS regression measuring mobility, SNS activation, PNS activation, and SUDS ratings. Moderation will be tested based on scores on anxiety, trauma, dissociation, and interoceptive awareness.
Primary Objective	Complete Master's thesis requirements for [name] investigating whether patterns of mobility map to physiological patterns and subjective experience when engaged in the defense cascade.
Secondary Objective(s)	I plan to submit a paper for publication in psychology peer-reviewed research journal as well as to use the data for poster presentations at conferences such as the Society for Psychophysiological Research.
Study Population	Young adults
Sample Size	200 for online prescreen, 100 to be invited to lab
Research Intervention(s)/ Investigational Agent(s)	Research intervention/stimulus will be a series of videos and experiences all presented in a VR environment, with peripheral audio and tactile enhancement. Investigational agents will include surveys, collection of psychophysiological measures including ECG, ICG, EDA, and accelerometry, behavioral observations from participant video footage, and post-hoc interviews with participants.
Study Duration for Individual Participants	1.5 hours for online prescreen, 2 hours for in lab; total of 3.5 hours
Acronyms and Definitions	
VT: Virginia Tech VR: Virtual Reality MBL: Mind-Body Lab ECG: ElectroCardioGram ICG: Impedance CardioGraphy EDA: ElectroDermal Activity PEP: Pre-Ejection Period HF-HRV: High-Frequency Heart Rate Variability PTSD: PostTraumatic Stress Disorder ANS: Autonomic Nervous System SNS: Sympathetic Nervous System PNS: Parasympathetic Nervous system SUDS: Subjective Units of Distress Scale

2.0 Objectives

2.1 *Describe the purpose, specific aims, or objectives of this study:*

The objectives of this study are to map patterns of mobility to patterns of physiology and self-reported subjective experience during a perceived threat experience.

2.2 *State the hypotheses to be tested:*

Mobility will be moderately positively correlated with SNS activation and moderately negatively correlated with PNS activation.

Transitions in mobility will be supported by ANS coactivation.

SNS activation will be moderately positively correlated with SUDS scores.

3.0 Background

3.1 *Summarize the relevant prior research on this topic and gaps in current knowledge within the field of study:*

Defensive and survival behavior describes responses to perceived threat. Research in this area flourished in the 1990s and early 2000s, developing an empirically-validated model called the defense cascade (Lang, Bradley, & Cuthbert, 1997). This model has enormous potential to explain and predict behavior under stress and to improve psychotherapy. However, research on defensive behavior has stagnated over the last decade. I am proposing this research in hopes of breathing new life into this important but recently neglected area of research.

The defense cascade demonstrates six sequential survival strategies: freeze, flight, fight, fright, flag, and faint (Cannon, 1932, Blanchard & Blanchard, 1990, Bracha, 2004, Schauer & Elbert, 2010). Each stage is determined by a dynamic interaction with threat. Freeze, or attentive immobility, quiets the body to attend to a potential threat while minimizing predator detection of movement. As danger approaches, mobile defense is activated with flight, and continues into fight if escape options are eliminated. If the mobile defenses of flight or fight have failed, fright brings tonic immobility, preserving consciousness and muscle tone for vigilance and preparedness for the possibility of escape, while simultaneously quieting the movement and vocalization that would incite further predatory strike. In order to still the body during such seemingly terrifying moments, physiologically-driven changes include numbing physical pain (Ludäscher et al., 2007) and blunting emotions (Schmahl et al., 2006). If escape remains elusive, flag will reduce heart

rate to minimize blood loss from injury and transition to the final stage, faint (flaccid immobility), in which muscle tone and consciousness are lost. Faint conserves remaining resources for the potential of future escape, while maximizing dead-like appearance to become less interesting to a predatory threat.

The defense cascade illustrates dynamic switches between mobility and immobility. Yet in spite of its importance to defensive behavior, mobility has rarely been researched explicitly. Mobility therefore merits investigation as an explicit research variable.

Changes in mobility appear to be supported by the autonomic nervous system (ANS), which engages the sympathetic nervous system (SNS) to power mobile defenses (Cannon, 1932; Lang, Bradley, & Cuthbert, 1997) and the parasympathetic nervous system (PNS) for immobile defenses (Öst 1984; Kleinknecht, 1987; Bracha, 2004). A more exacting study of the literature suggests that changes in mobility are supported by coactivation of the SNS and PNS (Löw, Lang, Smith, & Bradley, 2008; Roelofs, Hagedaars & Stins, 2010), a finding that requires replication to validate.

ANS coactivation has been characterized as a “positive predictor of health” (Berntson, 2019). It appears to support oxytocin uptake, but only among socially-connected participants. Lonely participants given oxytocin showed an increase only in SNS activation (Norman et al., 2011). ANS patterns bear further research, revealing adaptive responding in times of danger and safety.

I propose to investigate the mobility and autonomic correlates of the defense cascade, and to examine a self-report measure of subjective experience that could be leveraged in both research and clinical settings.

3.2 *Describe any relevant preliminary data:*

N/A

3.3 *Based on the existing literature, provide the scientific or scholarly rationale for and significance of your research and how will it add to existing knowledge:*

The defense cascade illustrates that defensive behavior is more than just “fight or flight” - these mobile defenses are but two of six stages. The remaining four stages are immobile defenses, each serving a unique purpose: avoiding detection, minimizing predatory aggression, reducing blood loss, and conserving resources. Yet defensive behavior is too often conceptualized as a set of mobile behaviors - "immobile defense" is viewed as an oxymoron. This view has pervaded American culture,

celebrating “action heroes” and stigmatizing victims of violence who did not fight back, mistakenly implying that an absence of mobility is an absence of defense.

Research into human defensive and survival behavior provides clues about both psychopathology and resilience. Freeze characterizes transition from calm to anxious states. The mobile defenses of flight and fight underlie stress and anxiety including most phobias (Hoehn-Saric & McLeod, 1988), as well as hyperarousal in PTSD (Morris & Rao, 2013).

Dissociation can arise during fright and become a conditioned response after repeated experiences invoking the state (Adenauer, Catani, Keil, Aichinger, & Neuner, 2009). Non-suicidal self-injury involves willfully invoking the natural analgesia that comes with fright, providing temporary relief from physical and emotional pain (Schauer & Elbert, 2010). Faint is found in blood-injection-injury type-specific (BIITS) phobia in response to feared situations (Bracha, 2004). Trauma has the potential to engage all six stages of the defense cascade, and how far a person has moved through the stages can be a revealing descriptor of the traumatic experience (hyperarousal vs. dissociative-type). Finally, recovery from threat can help inform therapeutic practice with clients experiencing any of the aforementioned conditions.

In a setting without war, the applicability of survival behavior to modern psychology can sometimes be questioned. However, in responding to any challenge, human physiology has a limited repertoire that was shaped by an evolutionary history of avoiding life threats. Non-survival threats have the potency to activate the same physiological circuits used for survival threats, often deactivating cognitive circuits in the process (Van der Kolk, 1994; Lanius et al., 2002). Traditional cognitive-behavioral therapies that ignore physiologically-driven defensive behavior overlooks this driver of chronic stress, anxiety, and posttraumatic stress disorder (PTSD), with an estimated combined lifetime U.S. prevalence of 28.8% (Kessler et al., 2005).

Defensive and survival behavior not only allows humans to escape life-threatening situations but has also been proposed as the therapeutic link to resolving symptoms of PTSD and anxiety-related stress (Payne, Levine, & Crane-Godreau, 2015). Yet some of the most essential elements of survival behavior, its underlying physiology and accompanying subjective experience continue to be poorly understood and minimally incorporated into therapeutic settings.

4.0 Study Endpoints

*4.1 Describe the primary and secondary **study** endpoints. See links below for discussion of study endpoints and how they may differ from study*

objectives. These are most common in clinical trials but are sometimes applicable to other types of biomedical research, as well as social, behavioral, or educational research. See link below for a discussion.

https://docs.google.com/document/d/1Wocz7K7a0hCQJPP0_khh5l1SQQjhGDDGHzcOPRHR5Tw/edit?usp=sharing

Primary endpoint will be the Pearson's correlations between the following variables:

- Mobility in X, Y, and Z planes each with pre-ejection period (PEP)
- Mobility in X, Y, and Z planes each with phasic electrodermal activity (EDA)

Secondary endpoint will be the Pearson's correlations between the following variables:

- Mobility in X, Y, and Z planes each with HF-HRV
- PEP and Subjective Unites of Distress Scale (SUDS)
- EDA and SUDS
- HF-HRV and PEP during one minute intervals where mobility is transitioning

- 4.2 *Describe any primary or secondary **safety** endpoints. These should be included for all studies that are greater than minimal risk. (Minimal risk: The probability and magnitude of harm or discomfort anticipated in the research that are not greater in and of themselves than those ordinarily encountered in daily life or during the performance of routine physical or psychological examinations or tests.):*

In order to minimize dangers associated with disoriented movement in the VR environment, one research assistant will be assigned the role of participant spotter, attending to any unsafe movements that participants may attempt while navigating their virtual environment.

Experiencing VR can increase the risk of dizziness or nausea because of the discrepancy between the actual and the virtual environment. The consent form includes a description of this possibility and how the participant can address it if they do not have tolerance of such symptoms.

The probability of psychological discomfort is assessed to be the same or less than that of watching a horror movie or playing a horror video game.

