5.0 Study Design and Statistical Analysis Plan

- 5.1 *Describe the basic study design/approach (e.g., qualitative study using five focus groups of first year students to describe assimilation into the university community; randomized controlled trial of a behavioral change intervention to increase dietary intake of whole grains; pre- post-test evaluation of new pedagogical techniques to improve adult literacy):*

This will be a quantitative study examining variables indexing physiology, mobility, and subjective experience of participants as they are exposed to stimuli designed to move them through stages of the defense cascade.

- 5.2 *Describe corresponding data analysis plan/approach (e.g., content analysis of focus group transcripts; descriptive analysis followed by linear regression modeling; nonparametric analysis of pre- and post-test measures):*

Data will be analyzed using Pearson's correlations to examine degree of correspondence between primary variables of interest that index mobility, SNS, and PNS activation, as well as SUDS. Additionally, as time allows, moderation analysis will be conducted to determine if higher scores on trauma, PTSD, dissociation, anxiety, and BIITS phobia affect the overall patterns observed in the primary variables of interest.

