7.0 Study Intervention(s)/Investigational Agent(s)

7.1 *Describe the study interventions (including behavioral interventions) and/or investigational agents (e.g., drugs or devices) to be used in this study. Consider each of the items listed below:*

- *Drug/Device Handling: If the research involves drugs or devices, describe your plans to store, handle, and administer the drugs or devices so that they will be used only on subjects, and only by authorized investigators.*
- *Describe whether any of the following will be used: microwaves, X-rays, DEXA scans, general anesthesia, or sedation*

- *If control of the drugs or devices used in this protocol will be accomplished by following an established, approved organizational SOP (e.g., Research Pharmacy SOP for the Control of Investigational Drugs, etc.), please reference the SOP in this section.*

This study's intervention will be a series of video clips projected in a VR environment, combined with a threat scenario designed uniquely for the VR environment. Additional interventions will include an audio white noise stimulus, a tactile vibrational stimulus, and a post-stimulus debrief. Video clips will be viewed as if on a projector within the VR environment and will include: (1) an approximately 3-minute instructional video on the use of the SUDS rating system, (2) an approximately 4-minute non-narrated video depicting marine life in a sunny, non-threatening situation accompanied by a soothing musical score, and (3) a portion of the threat scenario begins with images projected on the virtual projector. Both (1) and (2) are vanilla baseline clips, designed to measure physiological and mobility responses in a non-threatening situation as a baseline. The unique VR scenario begins again by a presentation of stimuli as if projected on a movie screen within the VR environment. The culmination of this threat scenario depicts a creature emerging from the projected movie screen and appearing to approach the participant in the VR environment.

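### The protocol records a non-threat baseline for physiology and mobility, but no endpoint or analysis uses it, so correlations of threat-period values across people would mix stable differences with the threat response.

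*Protocol*

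**What the plan says.** Section 4.1 of the protocol lists the endpoints as Pearson correlations. The primary ones are "Mobility in X, Y, and Z planes each with pre-ejection period (PEP" and "Mobility in X, Y, and Z planes each with phasic electrodermal activity (EDA". The secondary ones include "Mobility in X, Y, and Z planes each with HF-HRV", PEP with SUDS, EDA with SUDS, and "HF-HRV and PEP during one minute intervals where mobility is transitioning". None is described as a change from baseline or as adjusted for baseline.

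Section 5.2, which falls under the heading that includes the statistical analysis plan, says: "Data will be analyzed using Pearson's correlations to examine degree of correspondence between primary variables of interest". The study summary in section 1.0 is slightly wider: "Data will be analyzed using correlational analyses and OLS regression measuring mobility, SNS activation, PNS activation, and SUDS ratings". It names no baseline term either.

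Section 7.1 describes an instruction video on SUDS ratings (about 3 minutes) and a marine-life video (about 4 minutes), and states: "Both (1) and (2) are vanilla baseline clips, designed to measure physiological and mobility responses in a non-threatening situation as a baseline". Section 8.1 starts physiological recording with the first of these clips. It takes the first SUDS rating after that clip and further ratings every minute from then on.

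The objective in section 2.1 concerns patterns during a perceived threat, and the hypotheses in section 2.2 are about SNS and PNS activation.

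**The concern.** A PEP, HF-HRV or accelerometer value taken under threat has two parts: what the person shows without any threat, and what the threat adds. The hypotheses are about the second part. With one value per person and no adjustment, two participants with the same response to the threat but different non-threat PEP are scored as having different SNS activation.

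Two things follow. If the stable part of one measure is unrelated to the other measure, it acts as noise and pulls the correlation toward zero. If the stable parts of the two measures are related to each other, the correlation partly describes how people differ at rest or in calm viewing, and it may be too high, too low or of the wrong sign for the threat response. In the second case even a clearly significant correlation would not bear on the hypothesis. The study already collects the data that would separate the two parts.

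**Working it through.** **Inputs from the protocol (section 14.1).** Target correlation 0.3, alpha 0.05, beta 0.20, n = 85. Sidedness is not stated.

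**The plan's own figure.** By the Fisher z approximation, two-sided:

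N = ((1.960 + 0.842) / atanh(0.3))² + 3, with atanh(0.3) = 0.3095, gives 84.93, rounded up to **85**. Power at 85 is Φ(0.3095 × √82 − 1.960) = 80.0%. The stated number reproduces. (One-sided, N would be 68.)

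**Inputs not in the documents (assumed).**
- The correlation between mobility and the threat-evoked part of the physiological measure is 0.30 in absolute value.
- The share s of between-person variance in the threat-period value that is stable: 20%, 50% or 70%.
- Reliability of the baseline as a measure of the stable part: 0.8.

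**Case 1: one measure carries stable variance, unrelated to mobility.** Threat-period value = stable part + response, so r_observed = 0.30 × √(1 − s). Power = Φ(atanh(r) × √82 − 1.960).

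| s | r observed | power at 85 |
|---|---|---|
| 20% | 0.30 × √0.8 = 0.27 | 70% |
| 50% | 0.30 × √0.5 = 0.21 | 50% |
| 70% | 0.30 × √0.3 = 0.16 | 32% |

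**Case 1 after adjustment for baseline.** The baseline removes 0.8 × s of the variance of the threat-period value, so the partial correlation is 0.30 × √(1 − s) / √(1 − 0.8s). With one covariate, power uses √81 in place of √82.

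| s | partial r | power at 85 |
|---|---|---|
| 20% | 0.30 × √(0.8/0.84) = 0.29 | 77% |
| 50% | 0.30 × √(0.5/0.60) = 0.27 | 72% |
| 70% | 0.30 × √(0.3/0.44) = 0.25 | 62% |

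**Case 2: both measures carry stable variance with the same share s, and the stable parts correlate at ρ.** Then r_observed = (1 − s) × 0.30 + s × ρ. At s = 50%:

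| ρ | r observed |
|---|---|
| −0.3 | 0.15 − 0.15 = 0.00 |
| 0 | 0.15 + 0 = 0.15 |
| 0.3 | 0.15 + 0.15 = 0.30 |
| 0.5 | 0.15 + 0.25 = 0.40 |

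The direction of the distortion is therefore not fixed. At s = 70% and ρ = −0.3 the sign reverses: 0.09 − 0.21 = −0.12.

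**Cost of the covariates.** If there is nothing to remove and r = 0.30 throughout, two covariates replace √82 by √80. Power at 85 goes from 80.0% to 79.1%.

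**Covariate or change score.** With equal variances and a baseline-to-threat correlation of c, a change score has variance 2(1 − c) relative to the unadjusted value, and the covariate residual has 1 − c². At c = 0.3 these are 1.40 and 0.91; at c = 0.7 they are 0.60 and 0.51. The change score adds variance whenever c is below 0.5; the covariate never does.

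**The case against.** The strongest reply is that the protocol never says the values are raw. Section 4.1 gives only variable names, the hypotheses speak of activation, and clips labelled as baseline suggest that some correction may be intended. Scoring detail is often left to a later plan. This stands in part: a reader might infer that the protocol has chosen unadjusted levels, but that is inferred from silence. It does not remove the point. The text that defines the primary endpoint, and the section that carries the analysis plan, both specify a plain correlation and give the baseline no role.

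A second reply is that the unit of analysis is open. SUDS is rated every minute and one secondary endpoint is built on one-minute intervals. A within-person analysis across calm and threat minutes would remove stable differences and would make use of the baseline clips. This is correct, and the point applies only to correlations across people. The sample size of 85, calculated for a single correlation, suggests one value per person but does not prove it.

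Four stronger readings are not supported:
- That EDA is affected like the rest. The primary EDA endpoint is phasic, so the slow tonic level is already set aside. People may still differ in phasic reactivity, and the EDA-with-SUDS line omits the word phasic.
- That stable differences must dilute the result. Case 2 shows that they can also leave it unchanged or inflate it.
- That the 80% power is wrong. Section 14.1 does not say whether 0.3 refers to raw or baseline-adjusted values, and the 85 reproduces.
- That a resting baseline was recorded expressly for adjusting the endpoints. Section 7.1 describes a vanilla video baseline and does not state how it is to be used.

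**Conclusion.** The point holds as a weakness in how the endpoints are defined. A baseline for physiology and mobility is deliberately recorded, no stated endpoint or analysis uses it, and the hypotheses concern a response that the unadjusted values do not isolate. It applies to PEP, HF-HRV and mobility, and less to phasic EDA.

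The size cannot be determined from the documents. The loss in Case 1 (r of 0.27 down to 0.16, power of 70% down to 32%) is an illustration. It rests on an assumed stable share of 20% to 70% in one measure only, no relation of that share to mobility, a response correlation of 0.30, and one value per person. Other assumptions give inflation instead. The change is worth making because it is a better analysis of data already in hand at almost no cost, not because the sample size has been shown to be inadequate.

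**What to change.** In sections 4.1 and 5.2, define each between-person endpoint as a partial correlation of threat-period values, or equivalently as an OLS regression with baseline covariates (OLS is already named in section 1.0). Adjust each of the two variables for its own value in the non-threat baseline. For the SUDS endpoints, use the ratings given during the marine video as the SUDS baseline. Prefer covariate adjustment to a simple change score, for the reason shown in the working.

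State which clip supplies the baseline. Section 7.1 names both, and the choice is the investigators'. The marine clip is a reasonable one, because the other is the SUDS instruction video and ends before the first rating is taken. State also that these endpoints use one threat-period value per person. If a within-person analysis is intended instead, say so, since it handles stable differences in another way.

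Cost: a wording change, up to two degrees of freedom per correlation (power 79.1% instead of 80.0% at r = 0.30 and n = 85) and slightly more analysis work. No new data are needed.

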The BioNomadix Non-Invasive Cardiac Output system will be used to gather ICG data, which provides one of two inputs to the calculation of PEP, an estimate of SNS control of the heart. The Biopac ECG100C and Biopac RSP100C and/or the BioNomadix RSP & ECG System will be used to gather respiration and ECG data, which provides the second of two inputs to the calculation of PEP. It is also used to calculate HF-HRV, an estimate of PNS control of the heart. The Biopac Tri-axial Accelerometer and/or the BioHarness Physiology Monitoring System and/or the BioNomadix Accelerometer System will be used to calculate participant mobility in X, Y, and Z planes. Finally, the Biopac EDA100C and/or the BioNomadix PPG & EDA System will be used as a second estimate of SNS activation using galvanic skin response, an SNS index not influenced by the cardiac system. Uncertainty about which units will be used (the "and/or" language above) are due to uncertainty at the time of this application about whether the BioNomadix units will be funded by pending applications for scholarship and lab funds. Nevertheless, all aforementioned units will be used in accordance with their approved and attended purposes.

Two Microsoft webcams will be used to collect video footage of the participants from two angles: one will record facial expressions, while the other will record from the participant's side for behavioral coding to assess degree to which the participant is exhibiting approach versus avoidance behavior.

A noise-cancelling wireless headset will be used to deliver the audio portion of the video clips and to deliver a 98 decibel burst of white noise with 0 ms rise time and 750 ms duration.

A vibrational unit will be used to deliver a 5 volt vibration to the neck of the participant. This voltage is roughly three times the intensity of the vibration delivered by a standard smart phone in "vibrate" mode.

An Oculus Quest or Oculus Go headset will be used to present the Virtual Reality portion of the experiment to participants.

7.4 If the drug is investigational (has an IND) or the device has an IDE or a claim of abbreviated IDE (non-significant risk device), include the following information:

- Identify the holder of the IND/IDE/abbreviated IDE.
- Explain procedures followed to comply with sponsor requirements for FDA regulated research for the following:

FDA Regulation	Applicable to:		
	IND Studies	IDE studies	Abbreviated IDE studies

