 - *Survey(s), including online surveys*
 - *Demographic questionnaire(s)*
 - *Interview guide(s), e.g., questions or pool of questions for semi-structured interviews*
 - *Focus group guide(s)*
 - *Other documents used to collect data*

Screening and demographic questionnaires, online surveys, and interview guide have all been uploaded to Protocol Management. Subjects will be instructed to remain seated throughout the procedure.

8.4 What data will you collect during the study and how you will obtain them? Please include descriptions of electronic data collection, database matching, and app-based data collection:

Self-report data will be collected prior to the intervention and will include the questionnaires, surveys, and interviews itemized in section 8.1 and uploaded to Protocol Management. This will be collected by asking participants to complete the questionnaires on a computer. VT's Qualtrics will be employed for this purpose and all answers will be maintained in the Qualtrics system.

Physiological data will be collected using the aforementioned physiological equipment and will include ECG, ICG, EDA, and mobility in X, Y, and Z planes. Acquiring physiological signals requires placement of the electrodes as follows:

ICG requires placement of 8 electrodes: 2 on each side of the neck and 2 on each side of the torso, under the arms. ECG requires placement of 3 electrodes: 1 on each side of the collarbone and one on the bottom left rib bone. EDA requires placement of 2 electrodes: one on the index finger and one on the middle finger, both on the non-dominant hand.

To prepare each site for electrode placement, cotton swabs with alcohol will be rubbed on the participant's skin to remove oils and ensure optimal conductivity of physiological signals. After placement of electrodes, a lead will be clipped to each electrode that connects to the appropriate Biopac module (i.e. ICG leads will be attached to the ICG device) to relay

the signal to the Biopac Amplifier, which in turn allows the AcqKnowledge software to display the physiological signal on the computer screen.

Self-report SUDS ratings will be entered on screen by participants at one-minute intervals during the stimulus presentation.

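### Both primary endpoints and the HF-HRV secondary endpoint correlate each accelerometer axis separately, although the hypothesis treats mobility as one quantity; mixed axis results would not answer it, and per-axis correlations may be diluted

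*Protocol*

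**What the plan says.** Section 4.1 lists two primary endpoints, both Pearson correlations: "Mobility in X, Y, and Z planes each with pre-ejection period (PEP" and "Mobility in X, Y, and Z planes each with phasic electrodermal activity (EDA". With three axes and two sympathetic indices this makes 3 × 2 = 6 primary correlations. A secondary endpoint has the same form: "Mobility in X, Y, and Z planes each with HF-HRV". The remaining endpoint that mentions movement, "HF-HRV and PEP during one minute intervals where mobility is transitioning", uses mobility only to select intervals and names no axis.

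The hypothesis in 2.2 reads "Mobility will be moderately positively correlated with SNS activation and moderately negatively correlated with PNS activation". It names no direction and no axis. The background in 3.1 likewise frames the construct as a contrast between moving and being immobile. No resultant, magnitude or composite measure of movement appears anywhere in the protocol.

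On the equipment, 7.3 states: "The Biopac Tri-axial Accelerometer and/or the BioHarness Physiology Monitoring System and/or the BioNomadix Accelerometer System will be used to calculate participant mobility". The same paragraph explains the open choice by doubt about "whether the BioNomadix units will be funded by pending applications for scholarship and lab funds". Section 8.4 introduces sensor placement with "Acquiring physiological signals requires placement of the electrodes as follows" and then gives sites for the ICG, ECG and EDA electrodes. It gives neither a site nor an orientation for the accelerometer.

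Section 14.1 sizes the study at 85 for a correlation of 0.3, with alpha 0.05 and beta 0.20.

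**The concern.** The hypothesis asks how much a person moves. Each primary endpoint asks how much acceleration falls along one sensor axis. The two agree only if every participant's movement divides among the axes in about the same way, and the protocol does nothing to secure that. A backward lean and a sideways turn of equal size load on different axes, and which axes depends on how the sensor is mounted.

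Two things are at stake. The first is interpretation: a clear correlation on X with nothing on Y or Z has no defined reading, because no axis has a stated anatomical meaning and no hypothesis is attached to any axis. This holds whatever the size of any dilution. The second is power: if the autonomic index follows total movement, a single axis is a partial proxy for it, and the correlation on that axis can be smaller than the 0.3 for which the study was sized.

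**Working it through.** **Inputs from the protocol (14.1).** Target correlation 0.3, alpha 0.05, power 1 − 0.20 = 0.80, N = 85. Sidedness is not stated.

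**Step 1: reproduce the stated sample size.** With the Fisher z approximation, two-sided:

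N = ((z for 1 − α/2 + z for power) / atanh(r))² + 3 = ((1.960 + 0.842) / 0.3095)² + 3 = 84.93, so 85.

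This matches the protocol. A one-sided test would need 68, so the stated figure is consistent with a two-sided test.

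**Step 2: check for reserve.** Power = Φ(atanh(r) × √(N − 3) − 1.960). At r = 0.30 and N = 85 this is Φ(0.3095 × √82 − 1.960) = Φ(2.803 − 1.960) = 80.0%. There is no margin, so any attenuation takes power below 80%.

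**Step 3: attenuation on a single axis.** Let k be the correlation between one axis and total movement. If the autonomic index is related to an axis only through total movement, then r(axis) = 0.30 × k. The documents give no value for k, so a range is shown:

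| k (assumed) | r on one axis | Power per axis at N = 85 | N for 80% power |
|---|---|---|---|
| 1.0 | 0.30 | 80% | 85 |
| 0.9 | 0.27 | 71% | 106 |
| 0.8 | 0.24 | 60% | 135 |
| 0.7 | 0.21 | 49% | 176 |

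For k = 0.9, for example: atanh(0.27) = 0.2769, 0.2769 × √82 = 2.507, and Φ(2.507 − 1.960) = 71%.

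**Step 4: what range of r is plausible.** An illustrative simulation gave each participant a total amount of movement and tied the autonomic index to it at 0.30. It then varied the direction of movement and the sensor tilt between participants. With the same direction mix for everyone and no tilt, each axis kept 0.30. With a moderate spread of direction, the axes gave about 0.26 to 0.29. With a large spread they gave about 0.21 to 0.27. The combined magnitude stayed at about 0.30 throughout, as it must when the index is built on total movement. The spreads are assumptions, not protocol figures.

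**The case against.** The strongest reply is that the dilution depends on the model. If the autonomic index followed one direction, such as leaning toward or away from the approaching creature, that axis would carry the 0.30 and the combined magnitude would be the diluted variable, at 0.30 × k by the same algebra. This is fair as statistics, and it is why the loss can only be stated conditionally. But a directional response is not what 2.2 hypothesises, and the protocol ties no axis to approach or avoidance, so the reply does not rescue the endpoint as written.

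Several stronger readings are tempting, and the documents do not support them:

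- **That the correlations are in fact diluted.** Participants are seated (8.3, 21.1), watch a virtual screen and are reminded to keep still (16.1), all of which limits the spread of direction. The unit of analysis is not stated, and correlations within a person over time would not be affected by mounting differences between people. The loss can be near zero.
- **That axes differ between the permitted devices, or that devices will be mixed across participants.** Section 7.3 explains the open choice by pending funding. Mixing is not excluded, but it is not planned, and nothing says that the systems define their axes differently.
- **That gravity contaminates the axes.** A 10-degree tilt would shift a near-horizontal axis level by about 0.17 g (sin 10° = 0.174), but only if raw levels are analysed. Section 7.3 speaks of a calculated mobility, and filtering may be specified elsewhere.
- **That every endpoint involving mobility is affected.** The transition endpoint names no axis.

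The per-axis power figures also do not measure the chance of finding something. When the index follows total movement, the chance that at least one of three axes reaches an unadjusted 0.05 was about 72% in the most extreme setting and about 79% to 85% in four others. This stands, but it does not help: one significant axis out of three is exactly the result that the protocol has no way to read.

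**Conclusion.** The point holds in conditional form. The mismatch between a single, non-directional hypothesis and three separate axis correlations is plain on the face of 2.2 and 4.1, and it needs no numerical assumption. It is fixed in the protocol itself, not left to a later analysis document. The loss of power is a possibility, not a demonstrated fact. It requires that the autonomic index follow total movement and that direction or orientation vary. Under those conditions, values of k from 0.9 down to 0.7 take power per axis from 80% to between about 71% and 49%; with uniform direction and mounting there is essentially no loss. The study can run as written. This is a cheap improvement, not a fatal fault.

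**What to change.** In 4.1, replace the three per-axis variables in both primary endpoints and in the HF-HRV secondary endpoint with one pre-specified, orientation-free mobility index per epoch. One example is the root mean square of the three axes combined after the gravity component is removed. Report the separate axes as descriptive only. This leaves one primary correlation for each sympathetic index, two in place of six, each on the quantity that 2.2 names.

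In 7.3, once the funding outcome is known, commit to one accelerometer system for all participants, and state its body site and orientation there or beside the electrode sites in 8.4.

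The cost is a change of endpoint wording, one signal-processing step on data already to be recorded, and a placement instruction. The small downside is that direction of movement leaves the primary endpoint. Approach versus avoidance is already to be coded from the side video (7.3, 8.1, 8.4), so that information is kept.
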